Appendix A: Proposed Study Protocol

Step	Who
 Participant is compared against the study eligibility criteria: a) Not eligible – continue with standard practice b) Eligible Discuss eligibility with potential participant and provide study information sheet Obtain verbal consent for primary researcher to follow up regarding study participation Photograph wound as per study recommendations Complete Community Nursing admission assessment and Waterlow Risk Assessment NOTE: data obtained at this point is part of standard wound care practice for Community Nurses and this information would remain in the clinical file until consent obtained from the potential participant. 	Community Nurse
 2. Follow up with client to obtain consent for participation in study: a) If flagged for possible cognitive deficits then complete cognitive screen. b) If cognitive impairment determined then consent to be sought from Enduring Power of Attorney (evidence of this to be provided either sighting original or on clinical file). Consent obtained – continue with study protocol Consent not obtained – return to standard practice 	Primary Researcher
3. Participants will be entered into the study Sub-folder created for participant in "Photographs and Completed Assessments"	Primary Researcher
 4. Baseline data to be provided from clinical file baseline photograph Waterlow Risk Assessment Community Nursing admission assessment 	Community Nurses
 5. Initial Occupational Therapy assessment: To determine whether mattress overlay or mattress replacement will be appropriate. This will be dependent on the available surface for the mattress. To determine the appropriate size for the ROHO cushion To determine likelihood of long term equipment needs. If likely to need equipment on a long term basis (ie following the study end-point) then referral to be made to participant's preferred Occupational Therapy service. Referral at this point to is to minimise delays in service once participation in the study is finished and the allocated support surface is returned. 	Primary Researcher
 6. Pressure care education provided to participant: Provision of ACT Health brochure for preventing pressure injuries Verbal, face-to-face education to include discussion of the following principles: regular repositioning and offloading maintaining nutrition, including protein in diet maintaining skin health, including regular skin checks, managing continence and moisturising 	Primary Researcher
7. Participant provided with Baseline survey and Pain Scale	Primary Researcher

Step	Who
 8. Allocation of support surface Participant allocated to a treatment group using a random-number generator 1=active 2=reactive 	Primary Researcher
9. Provision of support surface (mattress and cushion) TARGET: Participant to be provided with allocated support surface within 2 days to minimise clinical risk of wound deteriorating	Primary Researcher
Participant will be provided with a mattress chosen from the allocated group based on availability. For example if participant is allocated to the 'active' group then they may be provided any of the mattresses listed in that group, based on availability.	
 The following considerations will be made when determining supplier of the allocated mattress: Is the required equipment clinically applicable? In some cases provision of a mattress may not be clinically applicable as a less invasive technique is often trialled first, such as heel elevation when the person has no previous history of pressure injuries. Similarly, not all people would require a cushion for sitting out of bed. In these instances, the allocated equipment will provide an appropriate level of care but may be marginally more intrusive than standard care. Mattress availability from the supplier. 	
 Suppliers of Support Surfaces: a) ACT Health Equipment Loan Service (ELS) – if allocated equipment is available and clinically applicable b) Astris Lifecare – if allocated equipment is not available from ELS or clinically applicable c) Invacare – if allocated equipment is not available from ELS or Astris Lifecare 	Information only
Active mattresses: a) Premium Digital 5 (overlay) – ELS, Invacare b) Premium Digital 9 (replacement) – ELS, Invacare c) Nimbus3 (replacement) – ELS d) Curocell Uno (replacement) – Astris e) Virtuoso (replacement) – Astris f) Salsbury (overlay) – Astris Reactive mattresses:	Information only
 g) ROHO Sections (1x foam and 3x ROHO sections, overlay) – ELS, Astris h) Atmosair (replacement) – ELS i) Softform Premier (replacement) – ELS, Invacare j) Curocell AREA (replacement) – Astris k) Curocell SAM (overlay) – ELS, Astris l) Pressureguard CFT (replacement) – Invacare m) BetterLiving Triple Layer (replacement) - Invacare 	
Cushion: 18"- 20" single valve high profile ROHO – ELS, Astris 10. Referral to be made to the appropriate supplier for provision of support surfaces:	Primary Researcher

Step	Who
b) Provision of support surface will be based on availability.c) Mattress and cushion to be provided and set-up	Primary Researcher ELS Staff Primary Researcher OR ELS Staff
type and ROHO cushion b) Sales Representative to choose mattress from pre-determined list based on mattress type and storeroom availability c) Mattress and ROHO cushion to be provided and set-up	Primary Researcher Sales Representative Primary Researcher OR Sales Representative Primary Researcher
 mattress and cushion, including contact information 12. Wound Management: Wound Management as per standard practice with the following additions: Photograph to be taken as per study recommendations at every dressing change Review participant for changes in function, including skin check for new pressure injuries if new pressure injury has developed this should be photographed and referred to Wound Nurse Practitioner and Primary Researcher for review for ethical impact Repeat Waterlow weekly 	Community Nurses
13. Photograph Management: Photograph will be placed in ACT Health e-note template for photographs in a clinical file with unique identifier only (photograph enlarged for one photograph per page). Document to be saved in PATHFILE (Saved as: "Photograph [Unique identifier] — [date YYMMDD]"), where date is date photo was taken	Community Nurses
	Tissue Viability Nurses
 Data Entry Data from RevPWAT to be entered into data spreadsheet on a weekly basis by Research Team Data from hard-copy surveys will be entered into Qualtrics by Research Team as they are completed (to be entered within one week of survey) 	Primary Researcher Research Team/Admin Support Research Team/Admin Support Primary Researcher

Step	Who
 Participant Completion of study endpoints will be determined by one of the following: e one week following complete healing of the initial pressure injury as determined by the RevPWAT (ie at the point when Community Nursing would be leaving the dressing on for a week – PWAT score of 0 for all subscores except subscore 8, where a score of up to 2 can be permissable) e weeks following the provision of the mattress e removed from the allocated surface – for example by request, move areas, hospitalisation, death, significant deterioration of existing wounds (such as progression to a Grade 3 pressure injury or development of an unstageable pressure injury) 	Information only
 Collect final data: Photograph initial pressure injury and any remaining pressure injuries as per study recommendations and store as per previous photographs (see Photograph Management) Final Waterlow Risk Assessment Review for changes in function, including a final skin check for additional pressure injuries not previously identified 	Community Nurses
17. Scoring of remaining photographs (see Assessment of wound photograph)	Tissue Viability Nurses
 18. Closure of study: Follow up with participant to ensure ongoing pressure care needs will be met by referral on to the appropriate services Organise for collection of the study mattress and cushion Thank participant for taking part 	Primary Researcher

Data/Secure Folder Management

Data will be kept on ACT Health servers in a secure folder. Access will be limited to the following people with additional restrictions in place:

- Research Team (primary researcher and supervisors, administration support for data entry) (RT)
- Community Nurses providing wound care (CN)
- Tissue Viability Nurses (TVN)

Breakdown of the folder will include the following sub-folders:

- Data Collation documents (additional password protection access for RT only)
 - Mattress allocation document
 - Spreadsheet for RevPWAT
 - o Spreadsheet for demographic data
- Photographs for assessment (this is where the CN will save the de-identified photograph e-note)
 - subfolders for each participant
- Completed Assessments
 - subfolder for each participant which will include
 - Photograph e-notes (TVN or CN responsibility)
 - Completed RevPWATs (TVN responsibility)
 - Completed Waterlows (CN responsibility)
 - Completed surveys (RT responsibility)
 - Completed consent forms (RT responsibility)

- Study Documents (read-and-print-only documents, RT able to modify folder contents)
 - How to Take Wound Photographs
 - How to Complete RevPWAT
 - Study Protocol
 - Information sheets
 - Blank Consent Forms
 - o Blank Baseline Survey
 - o Blank Follow-up Survey

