- 3. existing Grade 2 pressure injury the majority of pressure injuries managed in the community setting in ACT are Grade 1 or 2 (Lake, 2015).
- 4. have a bed that is appropriate for the test support surfaces
- 5. inability to reposition off the pressure injury—if the participant is able to offload the pressure injury then the support surface is only acting in a preventative manner rather than aiding wound healing.

Considered

Participants with Grade 1 pressure injuries will only be included if they also have a Grade 2 pressure injury, with the Grade 2 pressure injury being considered the primary pressure injury for the purposes of the study. Participants with Grade 1 pressure injuries only will be excluded as Grade 1 pressure injuries do not have any broken skin. It is expected that these will heal much faster and could skew the results with regards to effect size.

Exclusion Criteria

- existing Grade 3, Stage 4, Suspected Deep Tissue Injury or unstageable pressure injury these
 pressure injuries are not seen as frequently in the community setting (Lake, 2015) and have widely
 variable healing times, inclusion will skew the results.
- 2. Participation in the study during a previous episode of care

If accepted against the inclusion and exclusion criteria then prospective participants will be offered opportunity to participate in study – provided with consent paperwork and information package. Upon receipt of consent participant will be randomly allocated to one of three treatment arms.

Outcome Measures

Primary - Time to complete healing based on the Revised Photographic Wound Assessment Tool (Thompson, Gordey, Bowles, Parslow, & Houghton, 2013)

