All participants will receive education on general techniques to aid prevention of pressure injuries. This education will focus on behavioural changes rather than the provision of assistive technology. Adherence to recommendations from this education will impact on pressure injury healing as participants who are more compliant will be expected to have a quicker healing time. This adherence will be explored as part of the survey investigating the acceptability of the mattress.

Sleeping habits

The positions a participant sleeps in, their frequency of repositioning in bed and the location of the pressure injury will impact on the healing of the pressure injury. For example, a person with a sacral pressure injury who sleeps on their back with their head elevated is expected to take longer to heal their injury then a person with a hip pressure injury who sleeps in the same position. Baseline and changes in sleeping habits will be collected as part of the survey investigating the acceptability of the mattress.

Intervention

For details regarding the study protocol, please see Appendix A

Random allocation

Participants will be assigned to treatment groups using allocations in sealed envelopes:

- a) Experimental Group 1 reactive mattress/overlay
- b) Control Group active mattress/overlay

Support Surfaces

Mattresses

All mattresses used need to be supplier stated to be appropriate for Grade 2 pressure injuries.

Mattresses can be either full mattress replacements or mattress overlays. A high-quality randomised-controlled trial completed by Nixon et al. (2006) found no statistical difference between the effectiveness of alternating mattress replacements and alternating mattress overlays. In a community setting, the available beds for using a support surface will not always be hospital-type beds and will vary widely. There is likely to be occasions when use of a mattress replacement will not be possible. By grouping the treatment arms by mattress classification rather than a specific overlay or replacement, clinical applicability is increased, due to the increasing range of brands.

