- Patient's privacy should be respected at all times use drapes to obscure the view of body parts not involved with the wound.
 - Develop a consistent file labelling system and a secure back-up system with ample storage space.
 - Store de-identified photos in a secure location and develop or follow relevant site policies and procedures to ensure patient confidentiality is maintained.

Data Analysis

Sample size

Power calculations were unable to be completed due to unavailable data regarding standard deviations (SD) in previous literature. Articles reviewed either did not utilise similar outcome measures or did not report the SD due to non-normal distributions. A priori sample was determined for a total sample of n=80 to aim for a minimum final total sample of n=60 (to allow n=30 for each group, utilising the central limit theorem

(Field, 2013)) after allowing for withdrawals. Power calculations, including Cohen's d for effect size, will need to be completed at the completion of data collection.

Test inter-rater reliability of assessors of photographs

Although Thompson, et al. (2013) describe the inter-rater reliability of the RevPWAT, it is important to ensure the inter-rater reliability of the assessors with this wound type. Thompson, et al. (2013) tested reliability using a range of wound types that included pressure injuries however also had strict guidelines regarding the wounds at baseline to ensure good photographs were able to be taken, such as circumferential wounds (Thompson, et al., 2013). Photographs from the pilot study will be used to test inter-rater reliability of assessors.

Statistical Analysis

As the study has a non-inferiority design, data analysis will be completed twice and compared: one a Per Protocol analysis and one an Intention to Treat analysis. This is because each type of analysis biases different treatment groups (Scott, 2009) so by comparing the two analyses the results will be crossvalidated. For a similar reason, analysis will look at p-values of the relevant statistical tests as well as confidence intervals (where the confidence interval falling outside the pre-determined effect size will indicate equivalence or non-inferiority)(Greene, Morland, Durkalski, & Frueh, 2008).

Provided the relevant assumptions have been met, the following statistical tests will be completed:

Outcome Measure	Statistical Test			

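### The protocol contradicts itself on number of arms, method and timing of allocation, and Appendix A step 8 leaves concealment and protection against a redraw unassured

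*Protocol*

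**What the plan says.** Three places in the protocol describe allocation.

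- Recruitment, after the exclusion criteria: "Upon receipt of consent participant will be randomly allocated to one of three treatment arms".
- Intervention, Random allocation: "Participants will be assigned to treatment groups using allocations in sealed envelopes". Two groups follow, "Experimental Group 1 reactive mattress/overlay" and "Control Group active mattress/overlay".
- Appendix A, step 8: "Participant allocated to a treatment group using a random-number generator", with 1 for active and 2 for reactive. The responsible person is the Primary Researcher.

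Appendix A gives the same role step 2 ("Follow up with client to obtain consent for participation in study"), step 3 ("Participants will be entered into the study"), the initial occupational therapy assessment (step 5), the baseline survey and pain scale (step 7) and provision of the surface (step 9).

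The Data/Secure Folder Management section lists a mattress allocation document that only the Research Team can open. The Research Team includes the primary researcher. The Sample size section plans 80 participants for a final total of at least 60, "to allow n=30 for each group, utilising the central limit theorem".

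**The concern.** Mattress types are visibly different, and the protocol accepts that participants and treating clinicians cannot be blinded. Allocation is therefore one of the few safeguards left against selection bias, which the protocol says an RCT will eliminate. Its literature review also marks down other trials for unconcealed allocation.

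A team that follows Appendix A will use no envelopes, because Appendix A never mentions them. The person making the draw already knows the participant and the bed, and must then arrange supply to a target of 2 days. If an unwelcome draw can be repeated or set aside without trace, the two groups may differ for reasons other than chance, and no analysis can repair that.

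Timing matters too. Read literally, the Recruitment text allocates at consent. The baseline survey and pain score could then be given with the mattress type known, and the pain analysis compares scores before and after mattress provision.

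**Working it through.** **1. The texts side by side**

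| | Recruitment | Random allocation | Appendix A |
|---|---|---|---|
| Arms | three | two listed | two codes (1, 2) |
| Method | random, not specified | sealed envelopes | random-number generator |
| When | on receipt of consent | not stated | step 8; consent is step 2, baseline survey step 7 |
| Who | not stated | not stated | Primary Researcher |

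No third arm is defined anywhere. The sample size (2 × 30 = 60) and the comparisons in the Statistical Analysis table are also for two groups. So there is one wrong arm count, two methods not reconciled with each other, and two different times.

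**2. What protects the draw**

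The protocol does not say who prepares or holds the envelopes, or that a draw is logged or final. The allocation document is open to the person who enrols. The quarterly audit covers consent forms, photographs, assessments, surveys and mattress provision, but does not list allocation.

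**3. Does the method threaten 30 per group?**

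Inputs from the Sample size section: 80 planned, 60 final, 30 per group. The implied withdrawal rate is 1 − 60/80 = 25%, and 60/(1 − 0.25) = 80, so the figures agree. The rate is back-solved, so this shows consistency only. There is no power calculation to reproduce.

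Assumption: unrestricted 1:1 draws and independent withdrawals. The protocol does not say which kind of generator is meant.

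- Before withdrawals, P(both arms ≥ 30) = Σ C(80, x)/2^80 over x = 30 to 50 = 98.2%.
- With withdrawals, P(both arms ≥ 30) from 80 randomised:

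| Withdrawals | Simple draws | Exact 40:40 |
|---|---|---|
| 0% | 98.2% | 100% |
| 10% | 85.8% | 99.7% |
| 20% | 44.3% | 70.4% |
| 25% (implied) | 19.4% | 34.1% |

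- With exactly 60 finishers under simple draws, P(30:30) = C(60, 30)/2^60 = 10.3%. The expected smaller arm is 26.9, and the 95% range for one arm is 22 to 38.
- With exactly 60 random finishers from a perfect 40:40, P(30:30) = C(40, 30)²/C(80, 60) = 20.3%. Much of the shortfall therefore comes from a target with no slack, not from the generator.

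Cost of imbalance at 22:38: efficiency = (1/30 + 1/30)/(1/22 + 1/38) = 0.0667/0.0718 = 92.9%. The difference detectable with 80% power (two-sided 5%, assumed) goes from 2.80 × √(2/30) = 0.72 SD to 2.80 × √(1/22 + 1/38) = 0.75 SD.

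**4. Would small blocks help?**

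The Primary Researcher supplies the mattresses and so sees past allocations. Suppose that person always guesses the arm that is behind. In a block of 2 the expected number of correct guesses is 1/2 + 1 = 1.5. In a block of 4 it is 1/2 + 2/3 + 2/3 + 1 = 2.83. With the two sizes equally likely, the success rate is (1.5 + 2.83)/6 = 72%, against 50% for simple draws.

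**The case against.** The best defence is that the texts are loosely worded and do not really conflict. Envelopes can be filled from a generated sequence, so the body may describe concealment and Appendix A sequence generation. The third arm looks like an isolated slip. A fresh draw at step 8 comes after consent, entry, bed assessment and baseline survey, so it cannot be foreseen at enrolment. Community Nurses, not the researcher, check eligibility and record the baseline photograph and Waterlow score. Shortages are handled within the allocated arm, with three possible suppliers, and both arms include overlays and replacements.

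Much of this stands. A reader might infer that allocation is definitely unconcealed. The documents do not support that: sealed envelopes are specified in one place, and the draw described in the other is not predictable. A reader might also infer that the method will not give 30 per group. That fails too: the type of generator is not stated, unrestricted draws of 80 give at least 30 in each arm 98.2% of the time before withdrawals, and exact balance does not secure the target either. Nor do the product lists show that stock differs between arms, since no stock levels are given.

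The defence does not answer the central point. Step 8 describes allocating the participant with the generator, not filling envelopes, and an unforeseeable draw can still be repeated or overridden. If a list were made in advance and kept with the allocation document, the person enrolling could read it.

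**Conclusion.** The protocol is inconsistent on the number of arms, the method and the timing, and the passages must be reconciled. As Appendix A is written, concealment and protection against a redraw or override are not assured, because one person enrols, assesses, draws and supplies, with no locked or logged record. This is a gap in safeguards, not evidence that allocation has been or will be subverted, and the document gives no basis for a numerical estimate of bias. It still warrants correction before the first participant is randomised, since the remedy is nearly free and a compromised allocation cannot be undone later.

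Group balance is secondary. If draws are unrestricted and only 60 finish, an exact 30:30 split is unlikely (10.3%), but 22:38, the edge of the 95% range, costs only about 7% of efficiency. The target of 30 is a central-limit rule of thumb, not a power threshold.

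**What to change.** 1. In Recruitment, change the arm count to two and replace allocation on consent with allocation after the step 7 baseline survey.
2. State one method in Recruitment, Random allocation and Appendix A step 8: a two-arm 1:1 list, generated in advance by a team member who does not enrol (a supervisor or the administration support) and kept from the Primary Researcher. The allocations go into sequentially numbered, opaque, sealed envelopes.
3. Open each envelope only after step 7, and log participant code, envelope number, date and arm in a record that cannot be altered. Remove the draw by the Primary Researcher from step 8.
4. Keep the advance list out of any folder that the Primary Researcher can open, and amend the Data/Secure Folder Management section accordingly.
5. Restricted randomisation to limit imbalance is optional. If it is used, choose block sizes larger than 2 and 4 and do not disclose them to the person enrolling.

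The cost is protocol wording and about an hour of existing team time. Blocking, if chosen, gives up some unpredictability for a small gain in precision.

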Nixon et al (2006) Pressure relieving support surfaces: A randomised evaluation	To determine differences between alternating pressure overlays and alternating pressure mattresses as well as to investigate the impact of PIs on patients' wellbeing.	RCT in 11 hospital-based research centres across England Inclusion criteria: - aged ≥ 55 yrs - written informed consent obtained - acute patients with expected LOS of ≥ 7days and who were bedfast or chairfast and immobile or had very limited mobility and/or had a pre-existing G2 PIs on admission - OR surgical patients who were undergoing a surgical procedure with an average LOS of ≥ 7days and/or expected to be bedfast or chairfast and immobile or to have very limited mobility for at least 3 days post-op	Participants from acute or aged care wards Mean age = 75.2 yrs 5.6% participants had a pre-existing G2 PIs Group A: mattress replacement n= 982 Group B: mattress overlay n= 989 Mattresses varied between settings but had strict specifications to be adhered to preventing inclusion of hybrid mattresses	Twice weekly Skin assessment Twice weekly Braden Scale Twice weekly review of mattress to determine if changed, if working correctly and record reason for change All participants were provided with a high-spec foam mattress for 3 days following trial completion. Trial was completed when: Primary end-point – development of a new G2+ Pls on any skin site improved mobility and activity (Braden score of 3 or 4) transfer to non-participating ward discharge from hospital	Pls incidence G2+ on any skin site Time to healing of existing Pls Patient acceptability Cost-effectiveness	No statistically significant difference for PIs incidence – 10.3% Group A, 10.7% Group B, p=0.75 No statistically significant difference for time to healing – median time was 20 days for both groups, p=0.86 More participants allocated overlays requested changes due to dissatisfaction (23.3% vs 18.9%) - p= 0.02 More than one third of participants in both groups reported difficulties with bed mobility Cost analysis showed that mattress replacements were more cost-effective than overlays to an average saving	Standardised mattress overlays and replacements were not used, which could reduce the power of the study 25.7% of participants had 1 or more mattress changes which means that selection bias can be present for all data collected afterwards and can impact of a person's level of rick. This was

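### The overlay or replacement format is assessed before allocation, but the allocation ignores it and the supply steps do not clearly hold to it, so the arms can differ in format, mainly at the expense of the acceptability comparison

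*Protocol*

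**What the plan says.** In the main text (Support Surfaces, Mattresses), either format is allowed in either arm: "Mattresses can be either full mattress replacements or mattress overlays". Two reasons are given. One is a cited trial that "found no statistical difference between the effectiveness of alternating mattress replacements and alternating mattress overlays". The other is practical, since beds at home vary: "There is likely to be occasions when use of a mattress replacement will not be possible".

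Appendix A sets the order of events:

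- **Step 5**, by the primary researcher before allocation: "To determine whether mattress overlay or mattress replacement will be appropriate. This will be dependent on the available surface for the mattress".
- **Step 8**: allocation by random-number generator to active or reactive. No format stratum is named.
- **Step 9**: a target of provision within 2 days. Participants, in the example of the active group, "they may be provided any of the mattresses listed in that group, based on availability". The suppliers are tried in the order ACT Health Equipment Loan Service (ELS), Astris Lifecare, Invacare.
- **Step 10**, supplier route: "Sales Representative to choose mattress from pre-determined list based on mattress type and storeroom availability".

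The Appendix D evidence table, in its row for the trial cited in support of pooling, reports a median healing time of 20 days in both format groups (p=0.86). It also reports: "More participants allocated overlays requested changes due to dissatisfaction (23.3% vs 18.9%) - p= 0.02".

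**The concern.** The comparison of interest is active against reactive. Format is a second characteristic of the mattress, and the evidence offered for treating it as irrelevant comes from one of the two classes. Nothing is cited there on reactive overlays against reactive replacements, although the pooling rule covers the reactive arm.

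The same trial supports pooling for healing but not for acceptability. Comfort, transfers and ease of use are secondary outcomes here, and the protocol says it regards them as no less important than healing time. If one arm receives more overlays than the other, a difference in those ratings, or its absence, could partly reflect format.

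The steps also do not fit together. Step 5 produces a format decision for each participant. No later step, as far as the text can be read, says that this decision limits what is supplied.

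**Working it through.** **1. Does the cited format difference in acceptability re-check?** The evidence table gives 989 overlay and 982 replacement participants.

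- Counts: 0.233 × 989 ≈ 230 and 0.189 × 982 ≈ 186.
- Pooled proportion: (230 + 186)/(989 + 982) = 0.211.
- z = (0.2326 − 0.1894)/√[0.211 × 0.789 × (1/989 + 1/982)] = 2.35, two-sided p = 0.019 (0.022 with continuity correction).

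This agrees with the stated 0.02. The difference is 23.3 − 18.9 = 4.4 percentage points.

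**2. Format mix on the Step 9 lists** (overlays out of products listed):

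| Source | Active | Reactive |
|---|---|---|
| Full list | 2 of 6 | 2 of 7 |
| ELS | 1 of 3 | 2 of 4 |
| Astris Lifecare | 1 of 3 | 2 of 3 |
| Invacare | 1 of 2 | 0 of 3 |

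The full lists are close (33% and 29%), but the lists by supplier are not. If stock alone decided, and each listed product were equally likely (an assumption), the gap in overlay share, reactive minus active, would be 50 − 33 = +17 points through ELS, 67 − 33 = +33 through Astris and 0 − 50 = −50 through Invacare. A reactive participant assessed at Step 5 as needing an overlay cannot be given one from Invacare's listed products.

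**3. Chance imbalance if the Step 5 format is always supplied.** Format is then a baseline characteristic and the expected gap is zero. With unstratified allocation and the protocol's minimum of 30 per arm, take the overlay counts as two independent Binomial(30, p) variables. The overlay share p is not stated, so a range is assumed. A gap of 5 overlays is 5/30 = 17 points, and a gap of 6 is 6/30 = 20 points.

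| Assumed p | P(gap ≥ 5) | P(gap ≥ 6) |
|---|---|---|
| 0.2 | 0.145 | 0.075 |
| 0.3 | 0.204 | 0.120 |
| 0.4 | 0.235 | 0.147 |
| 0.5 | 0.245 | 0.155 |

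**4. Effect on an outcome.** The shift equals the gap in overlay share times the format effect. Borrowing the 4.4-point difference in dissatisfaction, which was observed for alternating surfaces in another setting:

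- 17-point gap: 5/30 × 4.4 = 0.7 points
- 20-point gap: 6/30 × 4.4 = 0.9 points
- 50-point gap: 0.50 × 4.4 = 2.2 points

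The format effect on this trial's Likert items, and on reactive surfaces, is not given in the protocol.

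**The case against.** Pooling is a reasoned choice for a pragmatic trial in homes with varied beds, and it compares mattress classes rather than products. For the primary outcome the cited trial is reassuring: healing time did not differ by format. Step 5 is tied to the participant's bed. If it binds, systematic imbalance largely disappears and what remains is the chance imbalance of any unstratified covariate, which is random error and not bias. The shifts in item 4 of the working are small. The opening of each Step 10 branch is missing from the text as extracted, so the mattress type passed to the supplier may include format. ELS is the first source, and the Invacare gap matters only when ELS and Astris both fail. Adjustment for format may be in an analysis plan that is not shown.

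Most of this stands, and it limits the point. It does not remove the wording of Step 9, which is legible and places no format limit on the choice, nor the absence of format from Step 8.

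A reader might infer three stronger things that the documents do not support:

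- **That overlays are shown to do worse on pressure injury incidence.** The evidence table has a pooled study with 3.6% vs 8.9% (p=0.047), but that sets a multi-stage mattress against a single-stage overlay, so format is mixed with inflation cycle. The single-stage comparison is 4.5% vs 8.9%, p=0.126, and incidence is not healing.
- **That a supplier's commercial interest steers the result.** Astris and Invacare each supply both arms, the list is fixed beforehand, and publication is agreed whatever the outcome. No incentive to favour an arm is shown.
- **That format confounding is built in.** It is possible under Step 9 as worded, but not if Step 5 binds.

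**Conclusion.** The point holds in a limited form. The evidence cited for pooling covers alternating surfaces only, and the same trial found a format difference in dissatisfaction. The protocol collects the format decision before allocation, does not use it at Step 8, and does not say whether it limits Steps 9 and 10. Format can therefore differ between arms, by chance and through supply after allocation.

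The concern is mainly for the acceptability outcomes; for healing the cited evidence shows no format difference. The size is unknown. The 7% to 16% probability of a gap of 20 points or more rests on assumed overlay shares of 20% to 50% and 30 per arm. The supplier gaps rest on equal likelihood of listed products. With the 4.4-point difference borrowed from the cited trial, the shift in dissatisfaction would be under 1 point for a 20-point gap. This is an inexpensive improvement and a contradiction to clear up, not a flaw that invalidates the comparison.

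**What to change.** 1. Record the Step 5 format before Step 8 and stratify the allocation by it (overlay, replacement). Use restricted lists, such as permuted blocks, within each stratum, because a simple random draw within strata does not balance them.
2. Include the Step 5 format as a factor in the healing and acceptability comparisons. Use the pre-allocation format, not the format delivered, since the latter arises after allocation and may depend on the arm.
3. Reconcile Steps 5, 9 and 10: state whether the Step 5 format limits the product supplied, and what happens when the supplier has no product of that format for the arm. Take account of the 2-day provision target. Which rule applies is for the investigators.
4. Set in advance how a product is picked when several listed ones are in stock.
5. In the Mattresses section, say that the cited evidence covers alternating surfaces, and report its acceptability result beside the effectiveness result.

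Cost: two allocation lists in place of one and a revised referral form. No new assessment is needed, since Step 5 is already carried out.
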